6.2. Preparation, Handling, Storage, and Accountability

The excipients used in the nirmatrelvir tablets/ritonavir capsules are safe for administration to pediatric participants.

Study intervention will be self-administered or administered to the participant by the caregiver.

1. The investigator or designee must confirm that appropriate conditions (eg, temperature) have been maintained during transit for all study interventions received and any discrepancies are reported and resolved before use of the study intervention.
2. Only participants enrolled in the study may receive study intervention and only authorized site staff may supply, prepare, and/or administer study intervention.
3. All study interventions must be stored in a secure, environmentally controlled, and monitored (manual or automated recording) area in accordance with the labeled storage conditions with access limited to the investigator and authorized site staff. At a minimum, daily minimum and maximum temperatures for all site storage locations must be documented and available upon request. Data for nonworking days must indicate the minimum and maximum temperatures since previously documented upon return to business.
4. Any excursions from the study intervention label storage conditions should be reported to Pfizer upon discovery along with actions taken. The site should actively pursue options for returning the study intervention to labeled storage conditions, as soon as possible. Once an excursion is identified, the study intervention must be quarantined and not used until Pfizer provides permission to use the study intervention. Specific details regarding the excursion definition and information to report for each excursion will be provided to the site in the IPM.
5. Any storage conditions stated in the SRSD will be superseded by the storage conditions stated on the label. Site staff will instruct participants on the proper storage requirements for take-home study intervention.
6. Study interventions should be stored in their original containers.
7. The investigator, institution, head of the medical institution (where applicable), or authorized site staff is responsible for study intervention accountability, reconciliation, and record maintenance (ie, receipt, reconciliation, and final disposition records), such as the IPAL or sponsor-approved equivalent. All study interventions will be accounted for using a study intervention accountability form/record. All study intervention containers that are taken home by the participant, both used and unused, must be returned to the investigator by the participant. **Returned study intervention must not be redispensed to the participants.**
8. Further guidance and information for the final disposition of unused study interventions are provided in the IPM. All destruction must be adequately documented. If destruction is

authorized to take place at the investigator site, the investigator must ensure that the materials are destroyed in compliance with applicable environmental regulations, institutional policy, and any special instructions provided by Pfizer.

Upon identification of a product complaint, notify the sponsor within 1 business day of discovery as described in the IPM.

6.2.1. Preparation and Dispensing

A qualified staff member will dispense nirmatrelvir/ritonavir using unique container numbers via an IRT system in the bottles and blister cards provided, according to the [SoA](#). A second staff member will verify the dispensing. The participant/caregiver should be instructed to maintain the product in the bottle and blister cards, as appropriate provided throughout the course of dosing and return the bottle and blister cards, as appropriate to the site at the next study visit.

6.3. Assignment to Study Intervention

Allocation of participants to treatment groups will proceed through the use of an IRT system. The site personnel (study coordinator or specified designee) will be required to enter or select information including but not limited to the user's ID and password, the protocol number, and the participant number. The site personnel will then be provided with a randomization number corresponding to the assigned treatment group, and DU or container number(s) when study intervention is being supplied via the IRT system. The IRT system will provide a confirmation report containing the participant number, randomization number, and DU or container number assigned. The confirmation report must be stored in the site's files.

Study intervention will be dispensed at the study visits summarized in the [SoA](#).

The study-specific IRT reference manual and IPM will provide the contact information and further details on the use of the IRT system.

6.4. Blinding

This is a double-blind study.

6.4.1. Blinding of Participants

Participants and their caregivers will be blinded to their assigned study intervention.

6.4.2. Blinding of Site Personnel

Investigators and other site staff will be blinded to participants' assigned study intervention.

Participants will be assigned to receive study intervention according to the assigned treatment group from the randomization scheme. Investigators will remain blinded to each participant's assigned study intervention throughout the course of the study.

In the event of a Quality Assurance audit, the auditor(s) will be allowed access to unblinded study intervention records at the site(s) to verify that randomization/dispensing has been done accurately.

6.4.3. Blinding of the Sponsor

Sponsor staff will be blinded to participants' assigned study intervention, except for designated individuals who may conduct unblinded reviews of the data if requested by regulatory authorities. An unblinded submissions team may be assembled to prepare unblinded analyses and documents to support regulatory activities that may be required while the study is ongoing.

Sponsor staff who are not directly involved with the conduct of this study will prepare analyses and documentation containing unblinded data while the study is ongoing to support interactions with the E-DMC.

The study will be unblinded after all participants complete the Day 34 visit (or ET prior to Day 34 visit) and analyses through Day 34, including the primary efficacy endpoint analyses, will be conducted.

Details of the unblinded sponsor staff supporting the data review(s) described above and the timing of unblinding will be outlined in the Unblinding Plan.

6.4.4. Breaking the Blind

The IRT will be programmed with blind-breaking instructions. In case of an emergency, the investigator has the sole responsibility for determining if unblinding of a participant's treatment assignment is warranted. Participant safety must always be the first consideration in making such a determination. If the investigator decides that unblinding is warranted, the investigator should make every effort to contact the study medical monitor prior to unblinding a participant's treatment assignment unless this could delay further management of the participant. If a participant's treatment assignment is unblinded, the sponsor must be notified within 24 hours after breaking the blind. The date and reason that the blind was broken must be recorded in the source documentation and CRF.

The study specific IRT reference manual and IPM will provide the contact information and further details on the use of the IRT system.

6.5. Study Intervention Compliance

Participants will use a participant-completed electronic dosing diary to record the date and time of their study intervention dosing, and will be educated at the time of first dose.

Site personnel will review the participant-completed electronic dosing diary daily during the study intervention period, preferably after the participant has self-administered the morning dose of nirmatrelvir/ritonavir. If any noncompliance with dosing is suspected, site personnel will promptly contact the participant by phone, to remind them of the relevant study procedures and/or entering the information in the electronic diary as applicable.

When participants are dosed at the site, they will receive study intervention directly from the investigator or designee, under medical supervision. The dose of study intervention and study participant identification will be confirmed at the time of dosing by a member of the study site staff other than the person administering the study intervention.

When participants self-administer study intervention(s) at home, compliance with study intervention will be assessed at each visit. Compliance will be assessed by delegated study personnel upon return of study intervention through counting returned tablets/capsules and direct questioning, if applicable during the site visits and documented in the source documents.

A record of the number of nirmatrelvir tablets/ritonavir capsules dispensed to and taken by each participant must be maintained and reconciled with study intervention and compliance records.

The following noncompliance cases will be considered medication errors (see Section 6.5):

- Participants interrupting study intervention for 2 consecutive doses;
- Participants taking either nirmatrelvir or ritonavir alone for 2 consecutive doses;
- Participants who have an overall study intervention compliance <80% or >115%.

In addition to the above listed-medication errors, any deviation from protocol-specified dosing (eg, missed single dose or partial dose) should be recorded as a protocol deviation and the investigator or designee is to counsel the participant/guardian and ensure steps are taken to improve compliance.

6.6. Dose Modification

Not applicable.

6.7. Continued Access to Study Intervention After the End of the Study

No study intervention will be provided to participants at the end of their study participation. It is expected that participants will be treated as required with standard-of-care treatments, as advised by their usual care physician.

6.8. Treatment of Overdose

Study sites should warn parents/caregivers to store the study intervention out of reach of children and to provide close supervision when intervention will be self-administered by the child.

For this study, any dose of nirmatrelvir greater than 900 mg (or any dose greater than 450 mg for participants on the reduced nirmatrelvir dose for moderate renal impairment) or ritonavir greater than 300 mg within a 24-hour time period will be considered an overdose.

There is no specific treatment for an overdose.

In the event of an overdose, the investigator should:

1. Contact the study medical monitor within 24 hours.

Closely monitor the participant for any AEs/SAEs and laboratory abnormalities as medically appropriate and at least until the next scheduled follow-up.

2. Document the quantity of the excess dose as well as the duration of the overdose in the CRF.
3. Overdose is reportable to Pfizer Safety **only when associated with an SAE**.

Decisions regarding dose interruptions or modifications will be made by the investigator in consultation with the study medical monitor as needed based on the clinical evaluation of the participant.

6.9. Prior and Concomitant Therapy

Permitted During the Study

Concomitant medications are permitted unless specifically listed as prohibited medication (see [Appendix 8](#)) or as defined in [Section 5.2](#). However, as described below, use of other specific COVID-19 treatments (eg, antivirals or monoclonal antibodies) are prohibited during the study.

Sites should consult with the sponsor if a new SoC option for COVID-19 becomes available after study initiation. The Investigator should ensure that any concomitant therapy is not a strong inducer of CYP3A4 or highly dependent on CYP3A4 for clearance. The Pfizer medical monitor should be consulted to review for potential drug-drug interactions (see [Appendix 8](#)).

Ritonavir is an inhibitor of CYP3A4 and may increase plasma concentrations of drugs that are primarily metabolized by CYP3A4. Participants will receive ritonavir for 5 days but as treatment is blinded, some concomitant medications ([Appendix 8, Table 4](#)) may require monitoring of drug levels, consideration of temporary withdrawal of the concomitant medication, or dose adjustment throughout the study treatment period and following completion of the blinded treatment duration period.

Prohibited During the Study

Participants are prohibited from receiving a non-study COVID-19 antiviral or monoclonal antibody therapy for COVID-19 within 14 days prior to randomization (excluding qualifying treatment with nirmatrelvir/ritonavir) and through completion of Day 34. Vaccination for COVID-19 is also prohibited within 14 days prior to randomization and through completion of Day 34.

As an exception, participants who progress to severe or critical COVID-19 will, however, be permitted to receive specific COVID-19 treatment(s) such as antiviral therapy or use of other treatments considered standard of care and the above restriction would not apply.

Nirmatrelvir and ritonavir are both primarily metabolized by CYP3A4. In addition, ritonavir is a strong inhibitor of CYP3A4. Therefore, concomitant use of medications that are strong

inducers of CYP3A4 and which are contraindicated in combination with nirmatrelvir/ritonavir (see [Appendix 8 Table 3](#)) are prohibited during study treatment. Some medications that are highly dependent on CYP3A4 for clearance are also contraindicated with nirmatrelvir/ritonavir (see [Appendix 8, Table 3](#)).

Some other medications that are not contraindicated but are highly dependent on CYP3A4 for clearance may require dose adjustment or additional monitoring. Refer to [Appendix 8 Table 4](#) for a nonexhaustive list of these medications and consult the Pfizer medical monitor for guidance on coadministration with nirmatrelvir/ritonavir.

Medications or substances that are strong inducers of CYP3A4 and that are contraindicated in combination with nirmatrelvir/ritonavir must be discontinued for an appropriate washout period prior to the first dose of nirmatrelvir/ritonavir and are prohibited for the duration of the study treatment period and for 4 days after the last dose of nirmatrelvir/ritonavir ([Appendix 8](#)). The appropriate washout period for CYP3A4 inducers should be determined based on the prescribing information for the concomitant medication and in consultation with the medical monitor.

7. DISCONTINUATION OF STUDY INTERVENTION AND PARTICIPANT DISCONTINUATION/WITHDRAWAL

7.1. Discontinuation of Study Intervention

It may be necessary for a participant to permanently discontinue study intervention. Reasons for permanent discontinuation of study intervention include the following:

- AE of Grade 3 severity or greater and considered by the investigator to be related to study intervention;
- SAE considered by the investigator to be related to study intervention;
- Requirement for prohibited concomitant medication;
- Study terminated by sponsor;
- Withdrawal by participant or legally authorized representative;
- If postscreening eGFR is <30 mL/min/1.73 m² (adult participants) or eCrCl is <30 mL/min (adolescent participants), the participant will be instructed to discontinue any remaining study intervention doses as soon as study staff become aware of the eGFR results.

In the event that a participant is hospitalized, study intervention may continue to be administered, as feasible, and based on medical judgment of the investigator.

Note that discontinuation of study intervention does not represent withdrawal from the study. If study intervention is permanently discontinued, the participant should remain in the study to be evaluated for all subsequent scheduled assessments. See the [SoA](#) for data to be

collected at the time of discontinuation of study intervention and follow-up for any further evaluations that need to be completed.

In the event of discontinuation of study intervention, it must be documented on the appropriate CRF/in the medical records whether the participant is discontinuing further receipt of study intervention or also from study procedures, posttreatment study follow-up, and/or future collection of additional information.

7.1.1. Pregnancy

For further details, refer to [Section 8.4.5.1](#).

7.2. Participant Discontinuation/Withdrawal From the Study

A participant may withdraw from the study at any time at their own request. Reasons for discontinuation from the study include the following:

- Refused further study procedures;
- Lost to follow up;
- Study terminated by sponsor;
- Withdrawal of consent/assent by parent/legal guardian or by a child who has provided assent during any phase of the study.

At the time of discontinuing from the study (if prior to Day 34), if possible, an early discontinuation visit should be conducted. See the [SoA](#) for assessments to be collected at the time of study discontinuation and follow-up and for any further evaluations that need to be completed.

The early discontinuation visit applies only to participants who are enrolled/randomized and then are prematurely withdrawn from the study. Participants should be questioned regarding their reason for withdrawal.

If a participant withdraws from the study, they may request destruction of any remaining samples taken and not tested, and the investigator must document any such requests in the site study records and notify the sponsor accordingly.

If the participant withdraws from the study and also withdraws consent (see Section 7.2.1) for disclosure of future information, no further evaluations will be performed and no additional data will be collected. The sponsor may retain and continue to use any data collected before such withdrawal of consent.

7.2.1. Withdrawal of Consent

Participants who request to discontinue receipt of study intervention will remain in the study and must continue to be followed for protocol-specified follow-up procedures. The only exception to this is when a participant specifically withdraws consent/assent for any further

contact with them or persons previously authorized by the participant to provide this information. Participants should notify the investigator in writing of the decision to withdraw consent from future follow-up, whenever possible. The withdrawal of consent should be explained in detail in the medical records by the investigator, as to whether the withdrawal is only from further receipt of study intervention or also from study procedures and/or posttreatment study follow-up, and entered on the appropriate CRF page. In the event that vital status (whether the participant is alive or dead) is being measured, publicly available information should be used to determine vital status only as appropriately directed in accordance with local law.

7.3. Lost to Follow-Up

A participant will be considered lost to follow-up if the participant repeatedly fails to return for scheduled visits and is unable to be contacted by the study site.

The following actions must be taken if a participant fails to be available for a required study visit:

- The site must attempt to contact the participant and reschedule the missed visit as soon as possible. Counsel the participant on the importance of maintaining the assigned visit schedule, and ascertain whether the participant wishes to and/or should continue in the study;
- Before a participant is deemed lost to follow-up, the investigator or designee must make every effort to regain contact with the participant (where possible, 3 telephone calls and, if necessary, a certified letter to the participant's last known mailing address or local equivalent methods). These contact attempts should be documented in the participant's medical record;
- Should the participant continue to be unreachable, the participant will be considered to have withdrawn from the study.
- In the event the participant is deemed unreachable, the investigator should utilize the contact information collected for the 2 individuals who can be contacted if the participant cannot be reached after multiple attempts.

8. STUDY ASSESSMENTS AND PROCEDURES

8.1. Administrative and Baseline Procedures

The investigator (or an appropriate delegate at the investigator site) must obtain a signed and dated ICD before performing any study-specific procedures.

Study procedures and their timing are summarized in the [SoA](#). Protocol waivers or exemptions are not allowed.

Adherence to the study design requirements, including those specified in the [SoA](#), is essential and required for study conduct.

All screening evaluations must be completed and reviewed to confirm that potential participants meet all eligibility criteria. The investigator will maintain a screening log to record details of all participants screened and to confirm eligibility or record reasons for screening failure, as applicable.

Every effort should be made to ensure that protocol-required tests and procedures are completed as described. However, it is anticipated that from time to time there may be circumstances outside the control of the investigator that make it unfeasible to perform the test. In these cases, the investigator must take all steps necessary to ensure the safety and well-being of the participant. When a protocol-required test cannot be performed, the investigator will document the reason for the missed test and any corrective and preventive actions that they have taken to ensure that required processes are adhered to as soon as possible. The study team must be informed of these incidents in a timely manner.

In the event a participant is hospitalized, study assessments should be performed as feasible. Procedures not performed due to hospitalizations will not be considered protocol deviations.

For samples being collected and shipped, detailed collection, processing, storage, and shipment instructions and contact information will be provided to the investigator site prior to initiation of the study.

The total blood sampling volume for individual participants in this study is approximately 160 mL. The actual collection times of blood sampling may change. Additional blood samples may be taken for safety assessments at times specified by Pfizer, provided the total volume taken during the study does not exceed 550 mL during any period of 56 consecutive days. For pediatric participants, every effort will be made to ensure that blood volume collections do not exceed 1% of the total blood volume at any single time and 3% of the total blood volume during any period of 4 weeks.

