5.1. Inclusion Criteria

Participants are eligible to be included in the study only if all of the following criteria apply:

Age and Sex:

1. Participants aged 12 years or older and weighing ≥ 40 kg at screening ([Section 10.10.1](#)).
 - Refer to [Appendix 4](#) for reproductive criteria for female ([Section 10.4.1](#)) participants.

Disease Characteristics:

2. Participants must have written documentation with patient-reported 100% compliance (ie, completed a 5 day course of nirmatrelvir/ritonavir). They must have symptom alleviation or resolution in COVID-19 signs/symptoms followed by a worsening (rebound) of signs/symptoms after completing an initial 5-day course of nirmatrelvir/ritonavir based on the judgement of both the participant and investigator ([Section 10.10.2](#)).
3. The onset of rebound in COVID-19 symptoms must occur within 2 weeks (14 days) after the completion of the initial 5-day course of nirmatrelvir/ritonavir.
4. Onset of rebound in signs/symptoms attributable to COVID-19 within 48 hours prior to randomization and ≥ 1 sign/symptom attributable to COVID-19 present on the day of randomization ([Section 10.10.2](#)).
5. SARS-CoV-2 infection as determined by rapid antigen testing in any specimen collected within 24 hours prior to randomization and collected within 2 weeks (14 days) after the completion of the initial 5-day treatment course of nirmatrelvir/ritonavir.
6. Has at least 1 characteristic or underlying medical condition associated with an increased risk of developing severe illness from COVID-19 ([Section 10.10.4](#)).

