8.6.2. Retained Research Samples for Genetics

A 4-mL blood sample optimized for DNA isolation Prep D1 will be collected according to the [SoA](#), as local regulations and IRBs/ECs allow.

Retained Research Samples may be used for research related to the study intervention(s) and COVID-19. Genes and other analytes (eg, proteins, RNA, nondrug metabolites) may be studied using the retained samples.

See [Appendix 5](#) for information regarding genetic research. Details on processes for collection and shipment of these samples can be found in the laboratory manual.

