8.7. Biomarkers

Collection of samples for biomarker research is also part of this study.

The following samples for biomarker research are required and will be collected from all participants in this study as specified in the [SoA](#):

- Nasopharyngeal swab will be collected to assess SARS-CoV-2 viral RNA level.
- A plasma sample will be collected to assess SARS-CoV-2 viral RNA level.
- Oropharyngeal swab will be collected to assess SARS-CoV-2 viral RNA level
- A plasma sample will be collected and may be used for protein biomarker analysis.
- Retained research samples.

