8.7.2. Viral RNA Assessment (Plasma)

A 6-mL blood sample will be collected per the [SoA](#) from participants and may be analyzed to measure SARS-CoV-2 RNA by RT-PCR. Residual samples may be utilized for viral sequencing, infectivity and phenotypic assays and additional molecular analysis. Host genetic analysis may also be performed.

Residuals of all samples may be stored for future research. Storage and shipping instructions will be in accordance with the laboratory manual.

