8.7.8. Retained Research Samples for Biomarkers

These Retained Research Samples will be collected in this study:

- 4-mL whole blood Prep B2.5 optimized for serum
- 2.5-mL whole blood Prep R1 optimized for RNA;
- 15-mL urine Prep M3.

Retained Research Samples will be collected as local regulations and IRB/ECs allow according to the [SoA](#).

Retained Research Samples may be used for research related to the study intervention(s) and COVID-19. Genes and other analytes (eg, proteins, RNA, nondrug metabolites) may be studied using the retained samples.

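### Near the 40 kg entry weight, the itemised research tubes alone exceed the protocol's own paediatric aim of 3% of blood volume in 4 weeks (assuming 70-80 mL/kg)

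*Protocol*

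**What the plan says.** Section 5.1 admits "Participants aged 12 years or older and weighing ≥ 40 kg at screening". Section 8.1 gives one figure for all ages: "The total blood sampling volume for individual participants in this study is approximately 160 mL". For paediatric participants it then says "every effort will be made to ensure that blood volume collections do not exceed 1% of the total blood volume at any single time", and adds a second limit of "3% of the total blood volume during any period of 4 weeks". The same section makes adherence to the Schedule of Activities mandatory and rules out waivers.

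Section 8.7 lists the NP and OP swabs, both plasma samples and the retained research samples, and says they "are required and will be collected from all participants in this study as specified in the" schedule. Volumes are printed for five blood tubes:

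- plasma viral RNA (8.7.2): "A 6-mL blood sample will be collected per the" schedule
- protein plasma (8.7.6.1): 6 mL
- genetics (8.6.2): "A 4-mL blood sample optimized for DNA isolation Prep D1 will be collected"
- retained serum (8.7.8): "4-mL whole blood Prep B2.5 optimized for serum"
- retained RNA, Prep R1 (8.7.8): 2.5 mL

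Sections 8.6.2 and 8.7.8 make the retained tubes subject to local regulation and IRB/EC permission. Haematology, chemistry and serology volumes are not given; Table 1 refers to the laboratory manual. Nothing in Table 1 or Sections 8.6-8.7 reduces, ranks or drops a tube by age or weight.

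**The concern.** The 4-week limit is a safeguard that the protocol sets for minors. If the default schedule takes more than the limit from the lightest eligible adolescents, a site that follows Table 1 exceeds it. A site that respects the limit must decide unaided which scheduled tubes to leave out. The protocol gives no order of priority, so nothing directs the omission towards an exploratory tube and away from a safety sample or the plasma RNA sample.

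**Working it through.** **Plan's own total.** The figure of about 160 mL can be neither reproduced nor refuted. Itemised blood through Day 34 is 42 mL plasma RNA (7 x 6), 30 mL protein plasma (5 x 6), 16 mL Prep D1 (4 x 4) and 26 mL Prep B2.5 plus R1 (4 x 6.5), which is 114 mL. The plasma RNA row of Table 1 reads one cell short, so Day 34 may also be marked; that would give 120 mL. The remaining 40-46 mL belongs to three haematology/chemistry draws (Days 1, 5, 34) and three serology draws (Days 1, 5, 28) of unstated volume.

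**Itemised blood, Days 1-28 (mL).** The Day 34 uncertainty does not enter here.

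| Day | Plasma RNA | Protein plasma | Prep D1 | B2.5 | R1 | Sum |
|---|---|---|---|---|---|---|
| 1 | 6 | 6 | 4 | 4 | 2.5 | 22.5 |
| 3 | 6 | | | | | 6 |
| 5 | 6 | 6 | 4 | 4 | 2.5 | 22.5 |
| 10 | 6 | | | | | 6 |
| 15 | 6 | 6 | 4 | 4 | 2.5 | 22.5 |
| 21 | 6 | | | | | 6 |
| 28 | 6 | 6 | | | | 12 |
| Total | 42 | 24 | 12 | 12 | 7.5 | **97.5** |

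**4-week limit.** Limit = 0.03 x weight x blood volume per kg. Blood volume per kg is an assumption: 70-80 mL/kg, with 65 and 85 as a wider check.

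- At 40 kg: 0.03 x 40 x 70 = 84 mL; 0.03 x 40 x 80 = 96 mL.
- Itemised share: 97.5/2800 = 3.48%; 97.5/3200 = 3.05%.
- Wider check: 97.5/2600 = 3.75% at 65 mL/kg; 97.5/3400 = 2.87% at 85 mL/kg.
- Weight below which 97.5 mL exceeds 3%: 97.5/(0.03 x 70) = 46.4 kg; 97.5/(0.03 x 80) = 40.6 kg.

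**Adding laboratory blood, if 160 mL is right.** With 46 mL unexplained, the least that can fall by Day 28 is two thirds, which is the case where it is all haematology and chemistry. That gives 97.5 + 30.7 = 128.2 mL, or 4.0-4.6% at 40 kg. With plasma RNA also on Day 34, the same bound is 97.5 + (2/3) x 40 = 124.2 mL (3.9-4.4%).

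**Readings that lower the itemised sum.**

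| Reading | mL | % at 70 mL/kg | % at 80 mL/kg |
|---|---|---|---|
| Prep D1 drawn once (97.5 - 8) | 89.5 | 3.20 | 2.80 |
| Day 28 visit on Day 29-30 (97.5 - 12) | 85.5 | 3.05 | 2.67 |
| Both (97.5 - 8 - 12) | 77.5 | 2.77 | 2.42 |
| No retained tubes (97.5 - 31.5) | 66 | 2.36 | 2.06 |

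At 80 mL/kg, the first two rows pass the limit once laboratory and serology blood exceeds 96 - 89.5 = 6.5 mL or 96 - 85.5 = 10.5 mL.

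**Per-draw limit.** At 40 kg, 1% is 28-32 mL. The largest itemised draw is 22.5 mL, or 0.80% and 0.70%. A breach needs more than 5.5-9.5 mL of laboratory blood at the same visit. Splitting the unexplained 40-46 mL evenly over three visits gives 35.8-37.8 mL (1.12-1.35%). If the total also budgets an early-termination visit, the draw is 26.9-28.4 mL (0.84-1.01%).

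**The case against.** The best reply is that the limit is worded as an effort, not a guarantee, and that the protocol leaves some room. Collection times may change, there is a process for tests that cannot be performed, and the retained tubes depend on local permission. Without them the itemised 4-week blood is 66 mL, under 3%. The genetics section speaks of one 4 mL sample and the Table 1 note of a single designated collection day, so one Prep D1 draw is a fair reading. At 80 mL/kg the margin is only 97.5 - 96 = 1.5 mL. Few participants may be concerned: adolescents enrol only where authorities approve (Section 10.10.1), and Germany enrols adults only (Section 10.9.2).

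Much of this stands, and it rules out three stronger readings. A reader might infer that the safeguard cannot be met; the effort wording and the conditional retained tubes do not support that. A reader might infer that the 1% limit is broken on Day 1; that rests on an even split of an approximate residual whose tube volumes are in a laboratory manual not available here. A reader might extend the 4-week breach to 53-61 kg (128.2 mL divided by 0.03 x 80 and 0.03 x 70); that rests on the same residual.

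The objection does not remove the central point. The condition on retained tubes is about local permission, not a child's weight, and Section 8.7 still lists them among the samples required from everyone. The missed-test process is for circumstances outside the investigator's control, not for a planned omission to protect a minor. Smaller tubes in the laboratory manual would contradict volumes printed in the protocol; the amendment history describes the 160 mL and the 6 mL protein volume as refined estimates from the central laboratory.

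**Conclusion.** The concern holds for the 4-week limit only. Followed as written, the schedule takes more than 3% of blood volume in 4 weeks from adolescents below about 41-46 kg on printed research volumes alone, with safety laboratory and serology blood still to come. The excess at 40 kg is 1.5-13.5 mL on those tubes. It is larger, at about 128 mL in all, if the approximate 160 mL total is accurate.

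The result rests on 70-80 mL/kg, which the documents do not give, and on the full schedule being drawn within Days 1-28. If Prep D1 is taken once, or the Day 28 visit falls on Day 29-30, itemised blood still exceeds the limit at 70 mL/kg, while at 80 mL/kg a breach depends on unstated laboratory volumes. If both apply, it depends on those volumes at either value. A per-draw breach remains possible but unproven. This is a change the sponsor should make for participant safety; it does not bear on the validity of the primary or secondary analyses.

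**What to change.** Reconcile Section 8.1 with Table 1 and Sections 8.6.2, 8.7, 8.7.6.1 and 8.7.8:

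1. Check every tube volume, including haematology, chemistry and serology, against the laboratory manual, and give the Day 1-28 and largest single-visit totals for a 40 kg participant together with the blood volume per kg used.
2. State that, for participants under 18 whose scheduled volume would exceed either limit, exploratory tubes are omitted in a fixed order: retained Prep D1, B2.5 and R1 first, then protein plasma. Safety laboratories, serology and plasma RNA are kept.
3. Qualify the requirement in Section 8.7 that these samples come from all participants.

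Dropping the retained tubes may not suffice: on the 160 mL total, at least about 66 + 30.7 = 96.7 mL would remain by Day 28. Dropping protein plasma as well leaves 42 mL of plasma RNA plus 30.7-46 mL of laboratory and serology blood, about 73-88 mL. The upper end is still above 84 mL, so step 1 is needed to confirm that the limit is kept.

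The cost is protocol wording, an adolescent kit configuration and the loss of some exploratory or retained samples from light adolescents. Section 9.3.6 does not plan retained-sample results for the CSR, and no endpoint in Section 3 is based on protein plasma.
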